#### **3.3 Discontinuation from Study Treatment**

Patients will be discontinued from study treatment for any of the following reasons:

- Disease progression
- Irreversible or intolerable toxicity or abnormal laboratory values thought to be related to drug toxicity
- Conditions requiring therapeutic intervention not permitted by the protocol
- Intercurrent illness (this will be at the investigator's discretion)
- Inability of the patient to comply with study requirements
- Patient requests to discontinue treatment
- Patient withdraws consent from the study
- Non-compliance/lost to follow-up
- Pregnancy

#### CONFIDENTIAL

STUDY DRUG(S): REGORAFENIB/AFATINIB/CABOZANTINIB INNOVATIONS STUDY NUMBER: PRO 10 FINAL PROTOCOL DATE: 6 MAY 2016 AMENDMENT NUMBER 2:23 JANUARY 2018 SARAH CANNON DEVELOPMENT

After discontinuation from protocol treatment, patients must be followed for adverse events (AEs) for 30 days after their last dose of study drug. All new AEs occurring during this period must be reported and followed until resolution, unless, in the opinion of the investigator, these values are not likely to improve, because of the underlying disease. In this case, the investigators must record his or her reasoning for this decision in the patients' medical records and as a comment in the electronic Case Report Form (eCRF).

All patients who have Grade 3 or 4 laboratory abnormalities (per National Cancer Institute Common Terminology Criteria for Adverse Events [NCI CTCAE] v 4.03 at the time of discontinuation must be followed until the laboratory values have returned to Grade 1 or 2, unless it is, in the opinion of the investigator, not likely that these values are to improve. In this case, the investigator must record his or her reasoning for making this decision in the patients' medical records and as a comment in the eCRF.

## 4. STUDY REGISTRATION

The patient must willingly consent after being informed of the procedures to be followed, the experimental nature of the treatment, potential benefits, treatment alternatives, side-effects, risks, and discomforts. Human protection committee (Institutional Review Board/Independent Ethics Committee [IRB/EC]) approval of this protocol and consent form is required. Eligible patients who wish to participate in the study will be enrolled into the study.

Registration must occur prior to the initiation of protocol therapy. Patients eligible to participate in the study may be enrolled through the Sarah Cannon Development Innovations Central Enrollment Desk. The enrollment desk may be reached by calling [name]. Registration may be done via [contact] Monday through Friday, 8:30 a.m. to 4:30 p.m., Central Standard Time. Patient registration will be confirmed via email within 24 hours, or by the next business day.

## 5. STUDY DESIGN

This four-arm pilot phase II study will evaluate the preliminary antitumor activity of selected commercially available molecularly matched targeted therapies in patients who have failed first line treatment for one of the following tumor types: (1) non-small cell lung cancer, (2) urothelial carcinoma, (3) non-colon gastrointestinal cancers, and (4) upper aerodigestive tract cancers. Patients will be profiled with next-generation sequencing technology results known prior to consideration for enrollment on this protocol. Patients with the specified tumor types demonstrating one of the genomic alterations described in Table 1 may be assessed for protocol eligibility and treatment. Patients with a genomic alteration that is not described in Table 1 but is covered by a targeted agent in Table 2 will also be eligible. All eligible patients will receive one of the FDA-approved targeted agents at the recommended dose outlined in Table 2. Dose modifications will be implemented based on criteria outlined in the product package insert for each individual agent. Patients will be re-evaluated for treatment response after receiving 8

CONFIDENTIAL

STUDY DRUG(S): REGORAFENIB/AFATINIB/CABOZANTINIB INNOVATIONS STUDY NUMBER: PRO 10 FINAL PROTOCOL DATE: 6 MAY 2016 AMENDMENT NUMBER 2:23 JANUARY 2018 SARAH CANNON DEVELOPMENT

weeks of oral therapy (with the exception of regorafenib which is dosed intermittently for 21 out of every 28 days). Response to therapy will be assigned using RECIST v1.1 (see Appendix E). Patients who have objective response (OR) or stable disease (SD) will continue treatment with re-evaluations every 8 weeks, until the time of tumor progression or intolerable treatment-related side effects. If a patient was not profiled with Foundation One® prior to study enrolment, Sarah Cannon Development Innovations shall use reasonable efforts to collect and send to Foundation Medicine adequate tumor tissue meeting the tissue specimen requirements for Foundation One® for retrospective profiling that will be completed and compared to the profiling report provided at study entry.

A total of 160 patients are planned to be enrolled on the trial (40 patients per study arm).

#### 5.1 Treatment Plan

#### 5.1.1 FDA-Approved Targeted Agents

The FDA-approved targeted agents that will be administered during the study are outlined in Table 2. Study drugs will be provided by the manufacturer and will not be billed to the patient's insurance as the proposed usage is considered off-label for the agent. The treating physician will decide which targeted agent will be prescribed based on the genomic alterations per tumor type and the targets listed in the package insert for each agent that are outlined in Tables 1 and 2. Patients with a genomic alteration that is not described in Table 1 but is covered by a targeted agent in Table 2 will also be eligible. The Medical Monitor will verify the genomic alteration and prescribed targeted agent when the patient is registered for the trial.

All patients entering this study will receive one of the targeted agents orally either daily continuously at the prescribed dose listed in Table 2 (except for regorafenib which is dosed daily for 21 out of every 28 days). Patients will be instructed to take the medication with or without food as directed in the product package insert. The time of day for administration of study drug should be consistent.

If the patient misses a dose of study drug, the patient should skip the missed dose and take the next dose as scheduled.

If vomiting occurs after taking the study medication, the patient should be instructed not to retake the dose. Patients should take the next scheduled dose of study drug. If vomiting persists the patient should contact the investigator.

No routine prophylactic antiemetics will be given. However, antiemetics may be administered for the treatment of nausea and vomiting when they occur, and may be given prophylactically afterwards.

Study drug compliance will be assessed by pill counts on Day 1 of each cycle. The research staff will count and document the amount of study drug taken and returned by the patient.

CONFIDENTIAL

STUDY DRUG(S): REGORAFENIB/AFATINIB/CABOZANTINIB INNOVATIONS STUDY NUMBER: PRO 10 FINAL PROTOCOL DATE: 6 MAY 2016 AMENDMENT NUMBER 2:23 JANUARY 2018 SARAH CANNON DEVELOPMENT

## 5.2 Treatment Duration

Patients will continue to receive treatment until disease progression, the patient requests to discontinue treatment, or the treating physician feels it is in the best interest of the patient to discontinue.

For the purposes of the study, a treatment cycle is defined as 28 days. Patients will be evaluated for toxicity at the start of each cycle. Every 2 cycles restaging will occur with imaging, laboratory tests will be assessed as defined in Appendix E.

#### 5.3 Concomitant Medications

Patients will be instructed not to take any additional medications during the course of the study without prior consultation with the research team. At each visit, the patient will be asked about any new medications he is taking or has taken after the start of the study drug.

#### 5.3.1 Permitted Concomitant Medications

No routine prophylactic antiemetics will be given. However, antiemetics may be administered for the treatment of nausea and vomiting when they occur, and may be given prophylactically afterwards. Anti-emetics may be administered according to standard practice guidelines.

Medications may be administered for maintenance of existing conditions prior to study enrollment or for a new condition that develops while on study, including but not limited to the following:

- Bisphosphonate use, as recommended according to practice guidelines
- Receptor activator of nuclear factor kappa-B ligand (RANKL) inhibitor use, as recommended according to practice guidelines

Other medications considered necessary for the patient's safety and well-being may be given at the discretion of the investigator.

#### 5.3.2 Prohibited Concomitant Medications

The following treatments are prohibited or should be used with caution while in this study:

- No other investigational therapy should be given to patients. No anticancer agents other than the study medications should be given to patients. If such agents are required for a patient, then the patient must first be withdrawn from the study.
- Herbal preparations/medications are not allowed throughout the study. These herbal medications include, but are not limited to: St. John's wort, kava, ephedra (ma huang), gingko biloba, dehydroepiandrosterone (DHEA), yohimbe, saw palmetto, and ginseng. Patients should stop using these herbal medications 7 days prior to first dose of study drug.
- Regorafenib and cabozantinib are metabolized by the cytochrome P450 (CYP) system. Therefore, drugs that are strong inducers or inhibitors of CYP3A4 should be avoided. These drugs are listed in Appendix F. Other potential drug interactions are described in the

CONFIDENTIAL	
STUDY DRUG(S): REGORAFENIB/AFATINIB/CABOZANTINIB	SARAH CANNON DEVELOPMENT
INNOVATIONS STUDY NUMBER: PRO 10	
FINAL PROTOCOL DATE: 6 MAY 2016	VERSION 3
Amendment Number 2:23 January 2018	

product package inserts for the individual agents and should be reviewed prior to the start of study treatment.

• Afatinib is a substrate of the P-glycoprotein transporter (MDR1). Caution should be exercised when combining afatinib with P-gp modulators. Below are the lists of potent P-gp inhibitors and inducers. Additional information can be found in the afatinib product package insert in Appendix H.

**Potent P-glycoprotein Inhibitors:** amiodarone, azithromycin, captopril, carvedilol, clarithromycin, conivaptan, cyclosporine, diltiazem, dronedarone, erythromycin, felodipine, itraconazole, ketoconazole, lopinavir, nelfinavir, ritonavir, quinidine, ranolazine, saquinavir, tacrolimus, ticagrelor, verapamil.

**Potent P-glycoprotein Inducers:** carbamazepine, phenytoin, rifampicin, St John's Wort, phenobarbital salt, tipranavir, ritonavir.

#### 6. **DOSE MODIFICATIONS**

If toxicity occurs, the toxicity will be graded utilizing the NCI CTCAE v4.03 (http://evs.nci.nih.gov/ftp1/CTCAE/CTCAE), and appropriate supportive care treatment will be administered to decrease the signs and symptoms thereof. Dose adjustments will be based on the organ system exhibiting the greatest degree of toxicity.

Doses of study drug will be modified based on hematologic and non-hematologic toxicity as outlined in the product package insert for each FDA-approved targeted agent. If dose reductions are necessary, they will be permanent for the remainder of the treatment. Any patient requiring a toxicity-related dose delay of more than 28 days from the intended day of the next scheduled dose must be discontinued from the study.

## 7. STUDY ASSESSMENTS AND EVALUATIONS

## 7.1 Overview

All patients should visit the study center on the days specified within this protocol. The complete Schedule of Assessments for this study is shown in Appendix D. The baseline physical examination, medical history, ECOG PS, and laboratory assessments should be done  $\leq$ 7 days prior to initiation of treatment. However, if these initial examinations are obtained within 72 hours of Cycle 1 Day 1 they do not have to be repeated. A pregnancy test must be performed within 72 hours of Cycle 1 Day 1. CT scans should be performed  $\leq$ 28 days prior to initiation of treatment, as should tumor markers, if appropriate.

CONFIDENTIAL

STUDY DRUG(S): REGORAFENIB/AFATINIB/CABOZANTINIB INNOVATIONS STUDY NUMBER: PRO 10 FINAL PROTOCOL DATE: 6 MAY 2016 AMENDMENT NUMBER 2:23 JANUARY 2018 SARAH CANNON DEVELOPMENT

#### 7.2 Baseline Study Assessments

The following information will be collected and procedures will be performed for each patient at screening:

- Written informed consent
- Medical history
- Physical examination, measurements of height (first visit), weight, and vital signs (resting heart rate, blood pressure [BP], respiratory rate, and oral temperature)
- ECOG performance status (see Appendix A)
- Concomitant medication review
- CBC (complete blood count) including hemoglobin, hematocrit, WBC with 3-part differential and platelets
- CMP to include: glucose, blood urea nitrogen (BUN), creatinine, sodium, potassium, chloride, calcium, carbon dioxide (CO2), alkaline phosphatase (ALT), AST, ALT, total bilirubin, total protein, and albumin plus magnesium.
- Coagulation analysis: prothrombin time (PT)/International Normalization Ratio (INR) and partial thromboplastin time (PTT)
- Serum or urine pregnancy test in women of child-bearing potential only (must be performed within 72 hours of Cycle 1 Day 1)
- CT scans of chest, abdomen and pelvis.
- Tumor markers (if applicable)
- Head CT or MRI scan [Required for patients with a history of treated brain metastases]

#### 7.3 Study Treatment Assessments

#### 7.3.1 Day 1 of each cycle

- Update of medical history
- Physical examination, including measurement of weight and vital signs
- ECOG performance status
- Adverse event (AE) assessment
- Concomitant medication review
- Study drug compliance review (Cycle 2 and beyond)
- CBC, including 3-part differential and platelets (may be done up to 72 hours prior to treatment)

#### CONFIDENTIAL

STUDY DRUG(S): REGORAFENIB/AFATINIB/CABOZANTINIBSARAH CANNON DEVELOPMENTINNOVATIONS STUDY NUMBER: PRO 10FINAL PROTOCOL DATE: 6 MAY 2016VERSION 3AMENDMENT NUMBER 2:23 JANUARY 2018VERSION 3

- CMP plus magnesium (may be done up to 72 hours prior to treatment)
- Serum or urine pregnancy test in women of child-bearing potential only
- Tumor markers (if applicable)
- CT scans of chest, abdomen, and pelvis (if abnormal at baseline) [Every 2 cycles]

#### 7.3.2 Day 15 of Cycle 1 Only

- AE assessment
- Concomitant medication review
- Vital signs
- Study drug compliance review
- CBC, including 3-part differential and platelets
- CMP plus magnesium

#### 7.4 End of Study Treatment

The follow-up evaluations required after treatment ends due to completion of the planned study treatment period, disease progression, or once the patient is discontinued due to unacceptable toxicity or decision to discontinue treatment by the patient or the study physician are specified in Appendix D.

If treatment is discontinued because of toxicity or any other reason(s) at a treatment visit and no study treatment is administered, that visit may fulfil the End-of-Treatment Visit.

After withdrawal from or completion of protocol treatment, patients must be followed for AEs for 30 calendar days after the last dose of study drug. The following assessments will be performed:

- Update of medical history
- Physical examination, including measurement of weight and vital signs
- ECOG performance status
- AE assessment
- Concomitant medication review
- Review study drug compliance with the patient, and collect unused study drug
- CBC, including 3-part differential and platelets
- CMP plus magnesium

#### CONFIDENTIAL

STUDY DRUG(S): REGORAFENIB/AFATINIB/CABOZANTINIB INNOVATIONS STUDY NUMBER: PRO 10 FINAL PROTOCOL DATE: 6 MAY 2016 AMENDMENT NUMBER 2:23 JANUARY 2018 SARAH CANNON DEVELOPMENT

Patients who discontinue study treatment prior to the occurrence of disease progression will be followed for disease assessment only every 3 months ( $\pm 1$  month) from the date of last dose of study drug until disease progression.

# 8. DRUG FORMULATION, AVAILABILITY, ADMINISTRATION, AND TOXICITY INFORMATION

#### 8.1 FDA-Approved Targeted Agents

Study Drug	Dosage Form and Strength	Manufacturer
Regorafenib	40 mg tablet	Bayer
Afatinib	40 mg, 30 mg, and 20 mg tablets	Boehringer Ingelheim
Cabozantinib	20 mg, 40 mg and 60 mg tablets	Exelixis

## 8.1.1 Labeling, Packaging, and Supply

The study drugs described in Section 8.1 will be supplied to Sarah Cannon Research Institute by the manufacturers.

At each visit, patients will be dispensed sufficient supplies until the next visit. Study drug compliance will be assessed at each patient visit. The research staff will count and document the amount of study drug taken and returned by the patient.

The immediate packaging will contain a statement to conform with U.S. Food and Drug Administration (FDA) Investigational New Drug (IND) requirements as follows: Caution: New Drug - Limited by Federal (or United States) law to investigational use.

All study drugs must be kept in a secure place at controlled room temperature. Storage conditions for each study drug are included on the product label and in the product package inserts included in Appendices G and H.

## 8.1.2 Precautions and Risks Associated with FDA-Approved Targeted Agents

Precautions and risks are described in the product package inserts for each drug included in Appendices G and H.

#### 8.2 Accountability for All Study drugs

The Principal Investigator (or designee) is responsible for accountability of all used and unused study drug supplies at the site.

	CONFIDENTIAL
STUDY DRUG(S): REGORAFENIB/AFATINIB/CABO	CANTINIB SARAH CANNON DEVELOPMENT
INNOVATIONS STUDY NUMBER: PRO 10	
FINAL PROTOCOL DATE: 6 MAY 2016	VERSION 3
Amendment Number 2:23 January 2018	

At the end of the study, all Sarah Cannon Development Innovations Drug Accountability Record Form(s) will be completed by the site and sent to the Sarah Cannon Development Innovations Regulatory Department. Study drug supplies must not be destroyed unless prior approval has been granted by the Sponsor or its representative. Please contact Sarah Cannon Development Innovations regarding disposal of any study drug.

#### 9. **RESPONSE EVALUATIONS AND MEASUREMENTS**

Response and progression will be evaluated in this study using the Response Evaluation Criteria in Solid Tumors (RECIST) Version 1.1 (see Appendix E). Lesions are either measurable or non-measurable according to the criteria. The term "evaluable" in reference to measurability will not be used, as it does not provide additional meaning or accuracy.

## **10. STATISTICAL CONSIDERATIONS**

#### 10.1 Statistical Design

This four-arm pilot phase II study will evaluate the preliminary antitumor activity of selected commercially available molecularly matched targeted therapies in patients who have failed first line treatment for one of the following tumor types: (1) non-small cell lung cancer, (2) urothelial carcinoma, (3) non-colon gastrointestinal cancers, and (4) upper aerodigestive tract cancers. Patients will be profiled with next-generation sequencing technology results known prior to consideration for enrolment on this protocol. Patients with the specified tumor types demonstrating one of the genomic alterations described in Table 1 may be assessed for protocol eligibility and treatment. Patients with a genomic alteration that is not described in Table 1 but is covered by a targeted agent in Table 2 will also be eligible. All eligible patients will receive one of the FDA-approved targeted agents at the recommended dose outlined in Table 2.

#### **Sample Size Considerations**

The design of this trial uses an exact single-stage design for each of the four arms. (A'Hern 2001) For this investigation, it has been determined that an ORR (CR + PR) of 10% or worse has low activity in line with standard of care. An ORR of 25% (or better) is considered to indicate interesting activity. Using a one-sided alpha of 5% and power of 80%, 40 evaluable patients will be required in each arm. A minimum of 8 responders in a particular arm would indicate that the corresponding tumor type would be worthy of further investigations.

#### 10.2 Data Analysis

Descriptive statistics, including mean, median, standard deviations and ranges for all continuous measures will be tabulated and reported. Percentages and frequencies for all categorical measures will also be presented. Time to events endpoints will be reported using Kaplan-Meier estimates, with 95% confidence intervals (CI) for median time to event.

CONFIDENTIAL	
STUDY DRUG(S): REGORAFENIB/AFATINIB/CABOZANTINIB	SARAH CANNON DEVELOPMENT
INNOVATIONS STUDY NUMBER: PRO 10	
FINAL PROTOCOL DATE: 6 MAY 2016	VERSION 3
Amendment Number 2:23 January 2018	

## **10.2.1** Demographics and Baseline Characteristics

Demographic and baseline disease characteristics will be summarized. Data to be tabulated will include demographic features such as age, sex and race, as well as disease-specific characteristics.

The number and percentages of patients screened, treated, and withdrawn from treatment/study for any reason will be presented overall and also by study arm.

## 10.2.2 Efficacy Analysis

All efficacy analyses will be performed using the Intent-To-Treat Population.

- Overall Response Rate (ORR) is defined as the proportion of patients with confirmed complete response (CR) or partial response (PR (i.e. 2 CRs or PRs at least 4 weeks apart) according to the RECIST v1.1.
- Clinical Benefit Rate (CBR) is defined as the proportion of patients with CR, PR or SD ≥ 6 months according to the RECIST v1.1.
  - For ORR and CBR, patients without a post-baseline tumor assessment will be classed as not evaluable (NE) and considered as non-responder.
- Time to treatment failure (TTF) is measured from the first day of treatment until the patient is removed from study for toxicity, disease progression, patient choice, or death.
- Progression Free Survival (PFS) is defined as the time from the first day of study drug administration (Day 1) to disease progression as defined by the RECIST v1.1, or death on study. Patients who are alive and free from disease progression will be censored at the date of last tumor assessment.

For ORR and CBR, the estimates and the associated 95% CI (based on the Clopper-Pearson method) in each treatment group will be calculated.

For PFS, Kaplan-Meier curves will be generated and the median time to event and the associated 95% CI will be provided.

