#### 2.2 Secondary Objectives

The secondary objectives of this study are to:

- Evaluate the clinical benefit rate (CR + PR + stable disease [SD] ≥ 6 months) in each patient population receiving targeted therapy based on relevant genomic alterations.
- Determine the time to treatment failure (measured from the first day of treatment until the patient is removed from study for toxicity, disease progression, patient choice, or death) in each patient population receiving targeted therapy based on relevant genomic alterations.
- To determine the progression free survival (PFS) in each patient population receiving targeted therapy based on relevant genomic alterations.

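### Time to treatment failure uses a closed list of four reasons and an end date at removal from study, so some treatment stops are left out or dated late and the endpoint reads too long

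*Combined protocol and SAP*

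**What the plan says.** TTF is a named secondary objective. The synopsis, Section 2.2 and Section 10.2.2 all start the clock on the first day of treatment and run it "until the patient is removed from study for toxicity, disease progression, patient choice, or death". There is no clause for other reasons.

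Section 3.3 has a longer list of reasons for stopping study treatment. It includes "Conditions requiring therapeutic intervention not permitted by the protocol", intercurrent illness, "Inability of the patient to comply with study requirements", "Non-compliance/lost to follow-up" and pregnancy. Section 5.2 also lets treatment end when the patient asks, "or the treating physician feels it is in the best interest of the patient to discontinue".

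Stopping drug does not end observation. Section 7.4 says: "Patients who discontinue study treatment prior to the occurrence of disease progression will be followed for disease assessment only every 3 months" (with a one-month window either side, counted from the last dose), until progression.

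Section 10.2 says time-to-event endpoints will be summarised by Kaplan-Meier with a 95% confidence interval for the median. The only censoring sentence in Section 10.2.2 belongs to PFS.

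**The concern.** TTF is normally meant to show how long patients can stay on a treatment, whatever ends it. Here the event definition does not match the protocol's own account of how treatment ends, and it is tied to leaving the study rather than stopping the drug.

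With Kaplan-Meier estimation, a patient whose stop is not a counted event must either be censored at that point or be carried forward to a later event. Stopping for intercurrent illness, for a prohibited therapy or on the physician's judgement is unlikely to be independent of how the patient is doing. Either handling therefore lengthens TTF compared with the time actually spent on drug.

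Each arm is analysed alone, so no comparison within the trial cancels the distortion. The definition also leaves room for two analysts to date the same patient's failure months apart.

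**Working it through.** **Step 1. Match the stop reasons to the event list.**

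| Reason for stopping treatment | Section | Among the four TTF reasons? |
|---|---|---|
| Disease progression | 3.3 | Yes |
| Toxicity | 3.3 | Yes |
| Patient request | 3.3 | Yes (patient choice) |
| Withdrawal of consent | 3.3 | Yes (patient choice) |
| Non-permitted therapy needed | 3.3 | No |
| Intercurrent illness | 3.3 | No |
| Inability to comply | 3.3 | No |
| Non-compliance or loss to follow-up | 3.3 | No |
| Pregnancy | 3.3 | No |
| Physician decision | 5.2 | No |

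Four of the nine reasons in Section 3.3 map to the list and five do not. Physician decision in Section 5.2 is a sixth. Section 5.3.2 gives a concrete case: a patient who needs another anticancer agent must first be withdrawn from the study, which is not necessarily for any of the four reasons.

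**Step 2. Take the two readings in turn.**

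- *Reading A, removal from study means off treatment.* Toxicity and patient-choice stops are dated correctly at drug stop. The six unlisted stops are not events. The plan does not say what happens to them; under Kaplan-Meier they would be censored.
- *Reading B, literal.* A patient who stops drug without progression remains in follow-up, so failure falls at progression or death. The first off-treatment assessment is due about 2 to 4 months after the last dose (3 months ± 1). A patient with an unlisted stop who stays in follow-up is then counted late, not left uncounted.

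For a patient who stays in follow-up, only one reading can apply.

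**Step 3. Illustrate the size.** The documents state no TTF figure to reproduce and no stop rates, so every rate below is an assumption. Take constant competing hazards. Let M be the median time to progression or death, s the share of drug stops that are for toxicity or patient choice, and u the share for unlisted reasons. Progression or death then accounts for a share 1 − s − u of stops, which gives:

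- all stops counted: median = M(1 − s − u)
- Reading A, unlisted stops censored: median = M(1 − s − u)/(1 − u), so the overstatement factor is 1/(1 − u)
- Reading B, everyone followed to progression or death at an unchanged hazard, with no delay in detection: median = M, so the factor is 1/(1 − s − u)

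Reading A, factor alone: u = 10% gives 1/0.90 = 1.11, and u = 20% gives 1/0.80 = 1.25. At u = 5% it is 1/0.95 = 1.05.

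Medians in months:

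| M | s | u | All stops | Reading A | Reading B |
|---|---|---|---|---|---|
| 3 | 10% | 5% | 2.55 | 2.68 | 3.0 |
| 3 | 20% | 20% | 1.80 | 2.25 | 3.0 |
| 5 | 10% | 5% | 4.25 | 4.47 | 5.0 |
| 5 | 20% | 20% | 3.00 | 3.75 | 5.0 |

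For example, with M = 3, s = u = 20%: 3 × 0.60 = 1.80, and 1.80/0.80 = 2.25. In an arm of 40 where all have stopped, u of 5-20% is 2 to 8 patients.

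**Step 4. Check what is not affected.** The sample size rests on ORR. With 40 patients and at least 8 responders, exact binomial calculation gives a one-sided alpha of 0.042 at 10% and power of 0.818 at 25%. Both meet the stated 5% and 80%, and neither uses TTF.

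**The case against.** The strongest reply is that the documents often say study where they mean treatment. The schedule footnote has patients followed for progression after study discontinuation. Section 6 has a patient with a toxicity delay of more than 28 days discontinued from the study. The off-treatment visit is an end-of-study evaluation in the schedule but falls under end of study treatment in Section 7.4. Read literally, removal from study for toxicity would hardly ever occur before progression, so a named event would be nearly empty. This stands, and it makes Reading B the less certain one. It does not settle the matter: Section 3.3 lists stopping treatment and withdrawing consent from the study as separate items, and Section 10.2.1 refers to withdrawal from treatment and study. Reading A leaves the omitted reasons in place anyway.

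It can also be said that pregnancy and loss to follow-up are not plainly failures of treatment, that patient choice might absorb some non-compliance, and that a cause-specific list is a legitimate convention. That is fair. But such a list needs a stated rule for the stops it leaves out, and there is none. Section 10.2.1 will tabulate withdrawals for any reason, which makes the omitted stops visible but does not correct the median.

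Two stronger conclusions are tempting. A reader might infer that the two faults add together; for patients who stay in follow-up they cannot, because each depends on a different reading. A reader might also infer that TTF will be overstated by half or more. Simulated factors of 1.49 to 1.82 do arise under Reading B for true medians of 3 to 4 months, but only if 30-40% of stops occur without progression, the further median to progression is 4 months and detection waits for a 3-monthly visit. With 10-20% such stops, the same model gives 1.14 to 1.33. The documents support none of these rates.

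**Conclusion.** The point holds in a conditional form. That six kinds of treatment stop lie outside the TTF event list is firm, since it follows from comparing the sections. That failures are dated late holds only on the literal reading of removal from study. On either reading TTF is biased upward for some patients, relative to time to permanent drug discontinuation.

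The size cannot be fixed from the documents. The 11-25% figure assumes exponential times, 10-20% of stops unlisted, and censoring of those stops. It is an illustration, not an estimate.

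The consequence is limited. TTF is secondary and descriptive, with no hypothesis or threshold attached. The background cites a TTF contrast of 5.2 vs 2.2 months from an outside study, and a reader might infer that this trial's TTF is to be judged against it. The plan sets out no such comparison. ORR, the 40 patients per arm and the 8-responder rule are unaffected. The definition should still be corrected before analysis.

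**What to change.** Change the wording in the synopsis, Section 2.2 and Section 10.2.2:

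- Define TTF as time from first dose to permanent discontinuation of study drug for any reason (all reasons in Sections 3.3 and 5.2) or death, whichever comes first.
- Censor only patients still on study drug at data cut-off, at that date.
- Date patients lost to follow-up by a rule stated in advance, for example an event at the last known dose.

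This changes an analysis definition only, not when any patient stops treatment. The cost is wording in three places. Section 7.4 already uses the date of last dose, and Section 10.2.1 already tabulates withdrawals. Reported TTF will be somewhat shorter than under the present wording.
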